## **2 STUDY DESIGN**

### **2.1 Study Overview**

This is a multicenter, open-label extension of Study 109MS202 that is designed to evaluate the long-term safety and efficacy of BG00012 in pediatric subjects.

### **2.2 Overall Study Duration and Follow-Up**

The study period will consist of enrollment, treatment, and follow-up. The study duration is approximately 104 weeks, consisting of a 4-week enrollment period (if the Final Study Visit from Study 109MS202 cannot be combined with the Baseline Visit for this study), a 96-week treatment period, and a Safety Follow-Up Visit up to 4 weeks after the last dose of study treatment. Unscheduled Relapse Assessment Visits and Lymphocyte Follow-Up Visits will be performed as necessary.

***End of Study for Subjects***

The end of the study is the last subject, last visit for final collection of data, which is the Safety Follow-Up Visit. This visit is up to 4 weeks after the last dose of study treatment.

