¹ An Unscheduled Relapse Assessment Visit will be conducted within 72 hours of symptom onset of a suspected relapse (i.e., new or recurrent neurologic symptom[s]).

² Discontinuation refers to discontinuation of study treatment. Withdrawal refers to withdrawal of subjects from the study. The Discontinuation/Withdrawal Visit should be conducted as soon as possible and no later than 4 weeks after the last dose of study treatment.

CONFIDENTIAL

The information contained herein may not be used, disclosed, or published without the written consent of Biogen MA Inc.

³ Subjects who complete, temporarily withhold, or permanently discontinue study treatment for any reason and have a lymphocyte count <LLN will continue protocol-required visits and assessments and be followed every 4 weeks for 24 weeks and then every 3 months (**unless clinically indicated more often or at the Investigator's discretion**) until the lymphocyte count is \geq LLN or for 52 weeks after the last dose, or until one of the following occurs: 1) the subject continues on commercial BG00012 following study withdrawal/completion, or 2) the subject is initiated on another MS disease-modifying therapy. Note: lymphocyte counts \geq LLN at 2 consecutive visits are required.

⁴ Vital signs include body temperature, pulse rate, and systolic/diastolic blood pressure measurements.

⁵ Hematology testing must be performed every 4 weeks in subjects with lymphocyte count <LLN.

⁶ Study treatment must be temporarily withheld or permanently discontinued if any of the laboratory values meet the criteria defined in the protocol.

⁷ For females of childbearing potential.

⁸ Urine cytology must be performed if a subject experiences hematuria (of unknown etiology) at 2 consecutive visits or at the Unscheduled Relapse Assessment Visit or the Discontinuation/Withdrawal Visit.

⁹ An MRI must not be performed within 30 days of receiving a course of steroids.

¹⁰ A brain MRI scan will be performed unless assessed in the last 30 days.

CONFIDENTIAL

The information contained herein may not be used, disclosed, or published without the written consent of Biogen MA Inc.

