7.2.3. Follow-Up

Subjects are to return to the study site for a follow-up visit 4 weeks after their last treatment visit (Visit 10 at Week 96 [± 5 days]).

Subjects who withdraw prematurely from the study will complete the Early Withdrawal Visit, which should be conducted as soon as possible and no later than 4 weeks after the subject's last dose of study treatment. Subjects who withdraw prematurely should be encouraged to complete the Safety Follow-Up Visit 4 weeks after the last dose of study treatment.

Subjects who complete, temporarily withhold, or permanently discontinue study treatment for any reason and have a lymphocyte count less than the lower limit of normal (LLN) will be followed every 4 weeks for 24 weeks and then every 3 months (**unless clinically indicated more often or at the Investigator's discretion**) until the lymphocyte count is \geq LLN or for 52 weeks after the last dose, or until one of the following occurs: 1) the subject continues on commercial BG00012 following study withdrawal/completion, or 2) the subject is initiated on another MS disease-modifying therapy.

CONFIDENTIAL

The information contained herein may not be used, disclosed, or published without the written consent of
Biogen MA Inc.

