7.5. End of Study

The end of study is last subject, last visit for final collection of data.

CONFIDENTIAL

The information contained herein may not be used, disclosed, or published without the written consent of
Biogen MA Inc.

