**Table 2: Additional Study Activities for Study 109MS311**

Tests and Assessments	Unscheduled Relapse Assessment Visit  (within 72 hours after symptom onset)	Discontinuation/ Withdrawal Visit  (as soon as possible but no later than 4 weeks after last dose of study treatment)	Lymphocyte Follow-Up Visit 
Physical Examination	X	X	X
Body Weight	X	X	X
Height		X	
Vital Signs 	X	X	X
12-Lead ECG		X	
Hematology 	X	X	X
Blood Chemistry 	X	X	
Urine Pregnancy Test 	X	X	
Urinalysis 	X	X	
PTH and Vitamin D Levels		X	
EDSS	X	X	
Brain MRI Scan 		X 	
Relapse Assessment	X		
Concomitant Therapy and Procedures		Monitor and record throughout the study	
AE/SAE Recording		Monitor and record throughout the study	

AE = adverse event; ECG = electrocardiogram; EDSS = Expanded Disability Status Scale; LLN = lower limit of normal; MRI = magnetic resonance imaging; PTH = parathyroid hormone; SAE = serious adverse event.

 An Unscheduled Relapse Assessment Visit will be conducted within 72 hours of symptom onset of a suspected relapse (i.e., new or recurrent neurologic symptom[s]).

 Discontinuation refers to discontinuation of study treatment. Withdrawal refers to withdrawal of subjects from the study. The Discontinuation/Withdrawal Visit should be conducted as soon as possible and no later than 4 weeks after the last dose of study treatment.

 Subjects who complete, temporarily withhold, or permanently discontinue study treatment for any reason and have a lymphocyte count <LLN will continue protocol-required visits and assessments and be followed every 4 weeks for 24 weeks and then every 3 months (unless clinically indicated more often or at the Investigator's discretion) until the lymphocyte count is  $\geq$ LLN or for 52 weeks after the last dose (whichever is sooner).

 Vital signs include body temperature, pulse rate, and systolic/diastolic blood pressure measurements.

 Hematology testing must be performed every 4 weeks in subjects with lymphocyte count <LLN

 Study treatment must be temporarily withheld or permanently discontinued if any of the laboratory values meet the criteria defined in the protocol.

 For females of childbearing potential.

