## **6 STATISTICAL ANALYSIS METHODS**

The statistical software, SAS®, will be used for all summaries and statistical analyses.

Statistical analyses will be descriptive in nature with appropriate measures of variation provided where applicable. For continuous endpoints, summary statistics will generally include the following: number of subjects with data, mean, standard deviation, median, and range. For categorical endpoints, summary statistics will generally include the frequency distribution of the analysis population.

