### **6.3.2.3 Clinical Laboratory Data**

The following clinical laboratory parameters are assessed per the protocol:

- Hematology: hemoglobin, hematocrit, red blood cell count, WBC count (with differential) and platelet count.
- Blood chemistry: albumin, sodium, potassium, chloride, total bilirubin, alkaline phosphatase, ALT, AST, GGT, blood urea nitrogen, creatinine, bicarbonate, calcium, magnesium, phosphate, uric acid, and glucose
- Vitamin D and PTH (Day 1 and Week 96 only)
- Urine and serum pregnancy tests

Each laboratory value for each subject will be flagged as ‘low’, ‘normal’, or ‘high’, relative to the parameter’s normal range. Each subject’s urinalysis values will be flagged as “positive”, “negative”, or if no value is available, “unknown”.

Shifts from baseline to post baseline (Week 4/early withdrawal) high/low status for all hematology and blood chemistry parameters, and shifts from baseline to high/positive status for urinalysis will be presented.

Summary statistics will also be provided for all absolute laboratory values as well as change from baseline. The summaries for laboratory data will be data from baseline to each time point, including early withdrawal. Graphs showing the mean or change from baseline values may be presented as well.

In addition to lymphocyte count data summarized at each timepoint on study treatment, lymphocyte count over time post-treatment and the time to recovery will be descriptively summarized for subjects who develop decreases in lymphocyte count (<LLN).

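### The SAP closes data collection at the Safety Follow-Up Visit although its lymphocyte follow-up runs to 52 weeks, and it does not say how unrecovered subjects enter time to recovery

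*SAP*

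**What the plan says.** Under End of Study for Subjects, SAP 2.2 says: "The end of the study is the last subject, last visit for final collection of data, which is the Safety Follow-Up Visit". The next sentence places that visit no more than 4 weeks after the last dose. Protocol 7.5 says only "The end of study is last subject, last visit for final collection of data", without tying it to a named visit.

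Other parts of the SAP expect later data:

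- SAP 2.2, in the paragraph just before, says "Lymphocyte Follow-Up Visits will be performed as necessary".
- SAP Table 2 footnote 3 follows subjects with a count below the lower limit of normal (LLN) every 4 weeks for 24 weeks and then 3-monthly, until the count is back at LLN or above "or for 52 weeks after the last dose (whichever is sooner").
- SAP 6.3.2.3 plans that "lymphocyte count over time post-treatment and the time to recovery will be descriptively summarized" for subjects who develop counts below LLN.

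That section gives no event definition, time origin or censoring rule. The general method in SAP 6 is that, for continuous endpoints, "summary statistics will generally include the following: number of subjects with data, mean, standard deviation, median, and range".

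Protocol v3.0 differs from SAP footnote 3 in two ways. It adds two ends of follow-up: "1) the subject continues on commercial BG00012 following study withdrawal/completion, or 2) the subject is initiated on another MS disease-modifying therapy". The notes to its Tables 2 and 4 also say that counts at or above "LLN at 2 consecutive visits are required".

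**The concern.** The end-of-study sentence names a final data point that most of the planned lymphocyte follow-up would miss. If it were applied to data cut-off, the time-to-recovery summary would lose most of its data.

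Separately, time to recovery is incomplete by design: follow-up stops at 52 weeks, or earlier if a subject goes on to commercial drug or another MS therapy. A subject still below LLN at that point has no recovery time. A mean or median over subjects with data then describes only those who recovered. The two ends of follow-up missing from the SAP footnote are natural censoring reasons for this analysis.

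The primary objective is long-term safety, and Protocol 5.3.2 links progressive multifocal leukoencephalopathy to deep, long-lasting low counts. The subjects with the slowest recovery are the ones the default summary would omit.

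**Working it through.** The plan gives no figure to reproduce: no recovery rate, no number below LLN and no sample size. The check is therefore a comparison of the texts, schedule arithmetic and a labelled illustration.

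**Texts.** SAP footnote 3 has the same stop rule as superseded protocol v2.0 Table 2 footnote 3, including the closing whichever-is-sooner clause. Visit frequency and the 52-week limit also agree with v3.0. The differences from v3.0 are the two-visit note and the two added ends of follow-up.

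**Schedule.** Every 4 weeks to Week 24 and then every 3 months (taken as 13 weeks) gives counts at Weeks 4, 8, 12, 16, 20, 24, 37 and 50: 8 visits, 7 of them after Week 4.

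- *Cut applied per subject:* a completer has about 1 of 8 counts. Two consecutive counts cannot occur before Week 8, so no confirmed recovery is possible. Subjects who stop treatment early but stay in the study (Protocol 10.1) are an exception.
- *Cut applied at study level:* collection closes up to 4 weeks after the last subject's last dose. A subject whose last dose was d weeks earlier has at most d + 4 weeks of post-dose data, which is less than 52 when d < 52 − 4 = 48.

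**Illustration.** Assume exponential recovery with true median m, S(t) = 2^(−t/m); recovery sustained once reached; all visits attended; no switching of therapy. For visits V(i):

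- Single count: event at V(i) with probability S(V(i−1)) − S(V(i)); share with no recovery time = S(last visit).
- Confirmed count: the same probabilities dated at the next visit; share with no recovery time = S(second-last visit).
- Recoverers-only median: first visit where cumulative probability reaches half the total recovered.
- Kaplan-Meier median: first visit where cumulative probability reaches 0.5.

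Example, m = 30, single count. Cumulative probabilities at the eight visits are 0.088, 0.169, 0.242, 0.309, 0.370, 0.426, 0.575 and 0.685. Half of 0.685 is 0.342, reached at Week 20; 0.5 is reached at Week 37. Gap 37 − 20 = 17 weeks.

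Same m, confirmed count. The total recovered is 0.575 and half is 0.288. This is passed at the fourth probability, now dated Week 20; 0.5 is passed at the seventh, now dated Week 50. Gap 50 − 20 = 30 weeks.

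Results for m = 10/15/23/30:

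| Visits | Event | No recovery time | Recoverers only | Kaplan-Meier | Gap (weeks) |
|---|---|---|---|---|---|
| 4 to 24, 37, 50 | single | 3/10/22/32% | 12/16/20/20 | 12/16/24/37 | 0/0/4/17 |
| 4 to 24, 37, 50 | confirmed | 8/18/33/43% | 16/16/20/20 | 16/20/37/50 | 0/4/17/30 |
| every 4 to 52 | single | 3/9/21/30% | 12/16/20/20 | 12/16/24/32 | 0/0/4/12 |
| every 4 to 52 | confirmed | 4/11/24/33% | 16/20/20/24 | 16/20/28/36 | 0/0/8/12 |

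The 4-weekly rows are needed because Table 2 footnote 5, in both documents, requires hematology every 4 weeks while the count is below LLN, whereas footnote 3 moves to 3-monthly visits after Week 24.

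**The case against.** Several stronger readings are tempting, and the documents do not support them.

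- *That the SAP cuts lymphocyte data at 4 weeks.* The sentence is worded as last subject, last visit, and the adjoining paragraph, footnote 3 and 6.3.2.3 all point the other way. No analysis section applies the cut. It may be loose text. What stands is that the SAP contradicts itself, and the heading, which refers to subjects, leaves a per-subject reading open.
- *That the SAP excludes unrecovered subjects.* It does not say so. SAP 6 says its statistics apply generally, and 6.3.2.3 asks only for a descriptive summary, which does not rule out censoring. Omission is the default consequence, not a stated rule.
- *That no confirming count will be taken.* The protocol governs visits, and the v3.0 table notes call for two. The SAP may predate v3.0: its Table 1 also lacks the Week 60 hematology entry. The front matter is not available to check this.
- *That the v3.0 body text contradicts its table notes throughout.* Section 11.2.5.1 and the withhold/discontinue paragraph of 11.2.5.2 point to Tables 2 and 4, which carry the note, and the recheck rule in 11.2.1 sits beside Table 4. Only 7.2.3 and the completer paragraph of 11.2.5.2 lack the note or a pointer.
- *That the gap is error against the true median.* It is a difference between two summaries of the same event. With a confirmed event on the coarse visits, Kaplan-Meier gives 16/20/37/50 against assumed true medians of 10/15/23/30, because recovery is dated late. The largest gap, 30 weeks, also depends on the 37/50 spacing.

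The objection that the summary is non-primary, and may concern very few subjects, stands in full.

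**Conclusion.** The point holds in limited form. The end-of-study clause conflicts with the SAP's own lymphocyte follow-up and planned summaries; footnote 3 is behind protocol v3.0; and the handling of unrecovered subjects is unspecified, with a default that would bias time to recovery downward when recovery is slow.

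The size cannot be known from the documents. In the illustration it runs from nothing at a true median of 10 weeks to between 12 and 30 weeks at a true median of 30, depending on event definition and visit spacing. This rests on exponential, sustained recovery, full attendance and no switching; switching would raise the share with no recovery time. It is a minor point about one descriptive safety summary and does not touch the primary endpoint.

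**What to change.** (a) SAP 2.2: delete the clause naming the Safety Follow-Up Visit, or state that data collection runs to the later of that visit and the last Lymphocyte Follow-Up Visit.

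(b) SAP Table 2 footnote 3: align with protocol v3.0. First the sponsor must reconcile the two-visit notes (Tables 2 and 4) with 7.2.3 and the completer paragraph of 11.2.5.2, and footnote 5's 4-weekly testing with the 3-monthly schedule.

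(c) SAP 6.3.2.3, for post-treatment recovery:

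- Measure time from last dose.
- Take the event definition from the reconciled protocol text and say which count dates it.
- Censor at the last count, or at the start of commercial BG00012 or another MS therapy, and note that this censoring may be informative.
- Summarise by Kaplan-Meier, or by a listing if few subjects are affected, with numbers recovered and unrecovered by reason.
- Keep the population already stated there, and list separately subjects who temporarily withheld and then resumed treatment.

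The cost is SAP wording and one table or listing from counts already planned. The drawback is that final lock may wait up to about 48 weeks (52 − 4) beyond the Safety Follow-Up Visit for affected subjects.

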### 3 STUDY ACTIVITIES

**Table 1: Schedule of Activities for 109MS311**

Tests and Assessments 	Year 1						Year 2					Safety Follow-Up Visit
	Baseline Visit (Day 1) 	Visit 1 (Week 12±5d)	Visit 2 (Week 16 ±5d)	Visit 3 (Week 24 ±5d)	Visit 4 (Week 36 ±5d)	Visit 5 (Week 48 ±5d)	Visit 6 (Week 60 ±5d)	Visit 7 (Week 64 ±5d)	Visit 8 (Week 72 ±5d)	Visit 9 (Week 84 ±5d)	Visit 10 (Week 96 ±5d)	
Informed Consent and Assent 	X											
Eligibility Criteria	X											
Medical History	X											
MS-Related Medical History 	X											
Physical Examination	X											X
Body Weight	X	X		X	X	X	X		X	X	X	X
Height	X			X		X			X		X	X
Vital Signs 	X	X		X	X	X			X	X	X	X
12-Lead ECG	X										X	X
Hematology	X	X		X	X	X			X	X	X	X
Blood Chemistry	X	X		X	X	X			X		X	X
Urine Pregnancy Test 	X	X		X	X	X			X	X	X	X
Urinalysis 	X	X		X	X	X			X		X	X
PTH and Vitamin D Levels	X					X					X	X
Brain MRI Scan 	X		X	X				X	X			
EDSS	X	X		X	X	X			X		X	
Dispense Study Treatment 	X	X		X	X	X	X		X	X		
Concomitant Therapy and Procedures Recording	Monitor and record throughout the study											
AE/SAE Reporting	Monitor and record throughout the study											

AE = adverse event; ECG = electrocardiogram; EDSS = Expanded Disability Status Scale; MRI = magnetic resonance imaging; MS = multiple sclerosis;  
PTH = parathyroid hormone; SAE = serious adverse event.

 Tests and assessments must be completed prior to study treatment dispensation.

 The Final Study Visit for Study 109MS202 will serve as the Baseline Visit for this extension study. The Final Study Visit from Study 109MS202 can be within 4 weeks of the Baseline Visit for Study 109MS311 if the 2 visits cannot be combined.

 Written informed consent from the subject's parents or legal guardians and assent from the subject, if appropriate, must be obtained prior to performing any study-related procedures.

 MS-related medical history will include complete MS history of disease, MS diagnostic criteria, MS signs and symptoms, and MS treatment history.

 Vital signs include body temperature, pulse rate, and systolic/diastolic blood pressure measurements.

 For females of child bearing potential. Results must be known prior to study treatment dispensation.

 Urine cytology must be performed at all visits indicated if a subject experiences hematuria (of unknown etiology) at 2 consecutive visits. If urine cytology is positive for malignant cells, the subject must permanently discontinue study treatment.

 Study treatment must be temporarily withheld or permanently discontinued if any of the laboratory values meet the criteria defined in the protocol.

 MRI must not be performed within 30 days of receiving a course of steroids.

 The time between the Week 24 MRI and the Week 16 MRI must be the same as the time between the Day 0 MRI and Week -8 MRI in Study 109MS202 within a window of  $\pm 3$  days. For example, if the Day 0 and Week -8 MRIs for a particular subject occurred 8 weeks apart in Study 109MS202, then the Week 24 MRI in Study 109MS311 should be 8 weeks  $\pm 3$  days after the Week 16 MRI. If necessary, the Week 24 MRI may be conducted separately from the Week 24 clinic visit. Similarly, the time between the Week 72 MRI and the Week 64 MRI must be the same as the time between the Day 0 MRI and Week -8 MRI in Study 109MS202 within a window of  $\pm 3$  days. If necessary, the Week 72 MRI may be conducted separately from the Week 72 clinic visit.

 Initial dispensation of study treatment may require an additional visit on or around Day 7. Laboratory results must be evaluated and eligibility confirmed prior to dispensation of study treatment.

**Table 2: Additional Study Activities for Study 109MS311**

Tests and Assessments	Unscheduled Relapse Assessment Visit  (within 72 hours after symptom onset)	Discontinuation/ Withdrawal Visit  (as soon as possible but no later than 4 weeks after last dose of study treatment)	Lymphocyte Follow-Up Visit 
Physical Examination	X	X	X
Body Weight	X	X	X
Height		X	
Vital Signs 	X	X	X
12-Lead ECG		X	
Hematology 	X	X	X
Blood Chemistry 	X	X	
Urine Pregnancy Test 	X	X	
Urinalysis 	X	X	
PTH and Vitamin D Levels		X	
EDSS	X	X	
Brain MRI Scan 		X 	
Relapse Assessment	X		
Concomitant Therapy and Procedures		Monitor and record throughout the study	
AE/SAE Recording		Monitor and record throughout the study	

AE = adverse event; ECG = electrocardiogram; EDSS = Expanded Disability Status Scale; LLN = lower limit of normal; MRI = magnetic resonance imaging; PTH = parathyroid hormone; SAE = serious adverse event.

 An Unscheduled Relapse Assessment Visit will be conducted within 72 hours of symptom onset of a suspected relapse (i.e., new or recurrent neurologic symptom[s]).

 Discontinuation refers to discontinuation of study treatment. Withdrawal refers to withdrawal of subjects from the study. The Discontinuation/Withdrawal Visit should be conducted as soon as possible and no later than 4 weeks after the last dose of study treatment.

 Subjects who complete, temporarily withhold, or permanently discontinue study treatment for any reason and have a lymphocyte count <LLN will continue protocol-required visits and assessments and be followed every 4 weeks for 24 weeks and then every 3 months (unless clinically indicated more often or at the Investigator's discretion) until the lymphocyte count is  $\geq$ LLN or for 52 weeks after the last dose (whichever is sooner).

 Vital signs include body temperature, pulse rate, and systolic/diastolic blood pressure measurements.

 Hematology testing must be performed every 4 weeks in subjects with lymphocyte count <LLN

 Study treatment must be temporarily withheld or permanently discontinued if any of the laboratory values meet the criteria defined in the protocol.

 For females of childbearing potential.

 Urine cytology must be performed if a subject experiences hematuria (of unknown etiology) at 2 consecutive visits or at the Unscheduled Relapse Assessment Visit or the Discontinuation/Withdrawal Visit.

 An MRI must not be performed within 30 days of receiving a course of steroids.

 A brain MRI scan will be performed unless assessed in the last 30 days.

